4.3 Safety Analysis Sets

The primary analysis set consists of all participants whose total exposure to the study drug BDQ was at the final implemented dose for their cohort for the protocol-specified period of BDQ administration. Participants who discontinued study drug due to toxicities will be considered a safety failure for this primary safety outcome measure* and will be considered an intercurrent event for the other primary safety outcome measures. Those who have had their doses adjusted as part of cohort management due to toxicities will be treated as safety failures* in the primary safety analysis. Participants who have been removed from study treatment for any reason (other than toxicity*) will be considered as having experienced an intercurrent event and will be included in the primary analysis dataset. These participants will be analyzed with the approach that those who experienced a primary safety outcome measure while on study drug will be considered as safety failure for that outcome measure. Those who were off study before the Week 24 visit due to reasons other than death will be included and will not be considered as a safety failure unless this was experienced before they were off study and while on study drug. The following sensitivity analyses will also be performed for participants who were off study before the Week 24 visit:

- The participant will be treated as safety failure (worst case)
- The participant will be excluded from the safety analysis set

Supplementary safety analysis dataset: All participants who were exposed to the study drug BDQ, including those who did not receive the final implemented dose evaluated in the study, as well as those whose dosing was amended based on PK considerations. The analysis approach will follow the same approach as that for the primary analysis set.

*Note that this refers to the relevant primary safety outcome (for example if the toxicity is “AEs of at least Grade 3 severity assessed by the Core Team to be at least possibly

related to study drug" then the participant will be considered a safety failure for this particular outcome measure only)

5 Report Contents

Detailed descriptions of the content of each of the following sections are given in the AIP.

1. Accrual
 - Screening (will be summarized in text only)
 - Number screened
 - Screening failure reasons
 - Enrollment
 - Number enrolled
2. Protocol deviations
 - Summary of reportable protocol deviations per IMPAACT Network Manual of Procedures
3. Baseline characteristics
4. Summary table for key characteristics, including sex, age, race, ethnicity, weight, height, Growth Z-scores, TB diagnostic category, TB disease type, and HIV status, TB Medication History, and key laboratory parameters
5. Study status
 - Number on treatment
 - Number off study prematurely, by reason and arm
 - Consort diagram (for final analyses only)
6. Safety Summary, in aggregate and by cohort
 - The proportions and listing of participants experiencing AE triggers as defined in protocol Section 9.5.2.
 - The listings and proportions of participants meeting the following primary endpoints:
 - Termination from treatment due to a drug-related AE
 - AEs of grade ≥ 3 severity
 - AEs of grade ≥ 3 severity assessed by the Core Team to be at least possibly related to the study drug
 - Absolute QTc interval ≥ 500 msec
 - Unstable dysrhythmias requiring hospitalization and treatment
 - Death (grade 5 AE)
 - Listing of QTcF over time (including mean QTcF across all participants per study week)
7. TB Treatment Outcome (included in SMC report if data are available)

8. HIV-1 RNA and CD4 summary statistics, and ARV experience for participants living with HIV
9. Data Completeness Report (no tables, summary will be provided in text)

6 Associated Documents

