3.1 Primary Outcome Measures (evaluated through week 24)

- Termination from treatment due to a drug-related AE
- AEs of \geq grade 3 severity
- AEs of \geq grade 3 severity assessed by the Core Team to be at least possibly related to the study drug
- Absolute QTcF interval \geq 500msec
- Unstable dysrhythmias requiring hospitalization and treatment
- Death (grade 5 AE)

3.2 Secondary Outcome Measures (evaluated through Week 96 / 72 weeks post BDQ discontinuation)

- AEs of \geq grade 3 severity

- AEs of \geq grade 3 severity assessed by the Core Team to be at least possibly related to the study drug
- Absolute QTcF interval \geq 500msec
- Unstable dysrhythmias requiring hospitalization and treatment
- Death (grade 5 AE)

NOTE: For the outcome measures 3.1 and 3.2 above, for creatinine events under protocol Version 1.0, serum creatinine grading for the study analyses will be based on the absolute value only as per the DAIDS AE Grading Table (Corrected Version 2.1, dated July 2017) and not on percentage change from the participant's baseline value. This is consistent with creatinine grading requirements in protocol Version 2.0.

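### Week 24 safety proportions can omit events that follow an early, non-toxicity stop of BDQ in children still on study, and no planned Week 24 sensitivity analysis shows the effect

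*SAP*

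**What the plan says.** SAP 3.1 lists six primary safety outcomes under the heading "Primary Outcome Measures (evaluated through week 24". It attaches no condition that the child be taking BDQ when the outcome occurs. SAP 4.1 describes the primary analyses as focused on the 24 weeks of BDQ treatment and reports proportions with exact 95% confidence intervals.

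SAP 4.3 sets the handling for children who stop early:

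- **Stopped for a non-toxicity reason:** an intercurrent event. The child stays in the primary set, and "those who experienced a primary safety outcome measure while on study drug will be considered as safety failure for that outcome measure".
- **Left the study before Week 24:** "Those who were off study before the Week 24 visit due to reasons other than death will be included", and such a child "will not be considered as a safety failure unless this was experienced before they were off study and while on study drug".
- **Stopped for toxicity:** a failure for the relevant outcome. The stop "will be considered an intercurrent event for the other primary safety outcome measures", with no strategy named for those other outcomes.

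Two sensitivity analyses follow, one treating the participant as a failure and one excluding the participant. Their scope is stated: "The following sensitivity analyses will also be performed for participants who were off study before the Week 24 visit". For the supplementary set of all exposed participants, "The analysis approach will follow the same approach as that for the primary analysis set".

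SAP 3.2 repeats five of the six outcomes (all but termination of treatment), "evaluated through Week 96 / 72 weeks post BDQ discontinuation". SAP 4.1 adds secondary analyses of all safety data to the end of the study.

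**The concern.** The outcome definition in 3.1 runs to Week 24. The counting rule in 4.3 appears to stop at the last dose for a child taken off BDQ early. A child who stops for, say, a non-safety reason and stays on study can then have a serious event inside the evaluation period and still be analysed as event-free.

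The Week 24 proportions and their intervals are the primary safety result and are to be posted as such. An on-drug count can only equal or fall below a count of all on-study events, so any difference makes the drug look safer. The usual safeguard is a sensitivity analysis that counts events regardless of discontinuation. The plan has none for children who are off drug but on study. The supplied text also does not say which day is the last on-drug day, so an event shortly after the last dose could be classified either way.

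**Working it through.** The plan states no figure for this point, so there is nothing to reproduce. The check is a reading of the rules against one case, followed by an illustration of size.

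**Inputs.** Outcomes and horizon: SAP 3.1. Counting rule, sensitivity analyses and supplementary set: SAP 4.3. Week 24 target day 168 and window days 161 to 195, applied to onset dates among others: SAP 4.2. Denominators 18 per cohort and 54 overall: SAP 2.1 and 2.3. These are planned PK-evaluable numbers, used as stand-ins because the size of the primary safety set is not given. Exact 95% intervals: SAP 4.1. Stopping weeks, event counts and risks below are assumptions.

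**Step 1. One child traced through the plan.** The child stops BDQ at Week 8 for a non-toxicity reason, stays on study, and has a first grade 3 AE at Week 14.

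| Analysis | Is the event counted? |
|---|---|
| Outcome definition, 3.1 | Yes, Week 14 is before Week 24 |
| Primary set, 4.3 | No, on the implied on-drug reading |
| Sensitivity analysis, worst case | Not applicable, child is not off study |
| Sensitivity analysis, exclusion | Not applicable, child is not off study |
| Supplementary set | No, same approach as primary |
| AE tabulations and listings, 4.1 | Possibly; no on-drug limit is stated |
| Week 96 outcomes (3.2) and all-data analyses (4.1) | Yes |

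Four of the six primary outcomes are exposed to this: any grade 3 or higher AE, drug-related grade 3 or higher AE, QTcF of at least 500 ms, and unstable dysrhythmia. Termination due to a drug-related AE marks the stop itself and cannot be missed this way. Death is taken up below.

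**Step 2. Follow-up time outside on-drug counting.** Days after last dose = E − 7 × (week of last dose), with E = 168 (target) or 195 (end of window).

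| Last dose | To day 168 | To day 195 |
|---|---|---|
| Week 8 | 168 − 56 = 112 (67%) | 195 − 56 = 139 (71%) |
| Week 12 | 168 − 84 = 84 (50%) | 195 − 84 = 111 (57%) |
| Week 20 | 168 − 140 = 28 (17%) | 195 − 140 = 55 (28%) |

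**Step 3. Effect of one uncounted event.** For x events in n, the Clopper-Pearson limits are the 2.5% quantile of Beta(x, n − x + 1) and the 97.5% quantile of Beta(x + 1, n − x). For x = 0 the lower limit is 0 and the upper limit is 1 − 0.025^(1/n).

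| n | Event counted | Event not counted |
|---|---|---|
| 18 | 1/18 = 5.6% (0.1 to 27.3) | 0/18 = 0% (0 to 18.5) |
| 54 | 1/54 = 1.9% (0.0 to 9.9) | 0/54 = 0% (0 to 6.6) |
| 54, five other events | 6/54 = 11.1% (4.2 to 22.6) | 5/54 = 9.3% (3.1 to 20.3) |

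**Step 4. Chance that at least one event is missed.** Assume a constant hazard, unchanged by stopping, and 24-week risk p. A child who stops at week w has first event off drug before Week 24 with probability m = (1 − p)^(w/24) − (1 − p). Among three such children the chance of missing at least one is 1 − (1 − m)³.

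- p = 10%, w = 16: m = 0.932 − 0.900 = 0.032, giving 9%.
- p = 30%, w = 8: m = 0.888 − 0.700 = 0.188, giving 46%.

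The number three is an assumption too. The range shows only that a few early stops would be enough to matter.

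**The case against.** The strongest reply is that nothing here is an error. SAP 3.1 gives a time horizon and 4.3 gives the handling of intercurrent events. An outcome assessed to Week 24 is compatible with a while-on-treatment strategy, and 4.1 points that way. This stands: the sections do not contradict each other, and on-drug counting may remain primary.

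Four stronger readings are tempting, and the documents do not support them:

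- **That 4.3 states an exclusion for children off drug but on study.** It does not. It says who is a failure and leaves the rest to inference. The inference is reasonable, since the on-drug phrase would otherwise do no work, but it is an inference.
- **That off-drug deaths disappear from every Week 24 result.** Section 4.3 excepts death from its off-study rule. A child who dies before the Week 24 visit is also off study by then, so the worst-case analysis makes that child a failure. What is missing is a plain statement that an off-drug death counts in the primary analysis.
- **That no Week 24 output shows these events.** The AE tabulations and the listings of grade 3 or higher events in 4.1 carry no on-drug limit. The gap concerns the primary outcome proportions and their intervals.
- **That the end of Week 24 is undefined.** SAP 4.2 assigns onset dates through day 195 to Week 24.

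It is also fair to say that the Analysis Implementation Plan, which is not supplied, may define the on-drug period. That would settle the boundary. Nothing in the SAP suggests that it adds a sensitivity analysis that 4.3 does not list.

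**Conclusion.** The point holds as a gap in the sensitivity analyses, and it should be fixed before the primary analysis. On the natural reading of 4.3, a non-fatal primary outcome after an early non-toxicity stop, in a child still on study, stays out of the Week 24 numerator, and no planned analysis of those proportions shows the difference. One such event is worth 5.6 percentage points in a cohort of 18 and 1.9 points among 54. The change is largest in appearance when it turns a single event into none.

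This rests on the implied on-drug limit, on 18 and 54 as stand-in denominators, and on assumed event counts. The documents give no rate of early stopping or of post-dose events, so the actual effect could be nil. The events are not hidden, because they enter the Week 96 and all-data secondary analyses. Confidence is medium.

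**What to change.** Keep on-drug counting as the primary approach if that is intended, and say so plainly for children off drug but on study. Then add to SAP 4.3:

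1. A Week 24 sensitivity analysis, for both the primary and the supplementary sets, counting every primary safety outcome from first dose through the Week 24 window (day 195 in 4.2) while the child is on study, whether or not BDQ was stopped.
2. The last on-drug day used for the on-drug count.
3. A statement that all deaths through Week 24 count as failures for the death outcome.

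The same edit could name the strategy for the other outcomes after a toxicity stop, but that is a wording matter.

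The cost is one extra programmed derivation and a few lines of text. The added proportions may be slightly less favourable. The analysis is informative only if AEs and ECGs are collected after early stopping. The visit schedule is not in the supplied text, so the team should confirm this first.

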Attachment 2: Timetable for primary analysis and manuscript preparation

Event	Responsible party	Weeks from primary completion date (PCD)
Primary completion date (PCD)		PCD
Clinical data entry complete	Sites	PCD + 2 weeks
Initial database clean complete	PDM and LDM	PCD + 13 weeks
Clinical database closure/freeze complete/eCRF sign-off by site investigators	PDM and Sites	PCD + 16 weeks
Clinical database lock and primary laboratory database lock	Chief Data Manager and LDM Leadership	PCD + 19 weeks
Primary analysis report to Protocol Chairs/Writing Team	Protocol statisticians	PCD + 27 weeks
ClinicalTrials.gov results for primary outcome measures due	Protocol statisticians	PCD + 52 weeks*

*The primary outcome measure results must be entered in clinicaltrials.gov exactly 1 year after the PCD.
